7.8 Statistical Analyses

Amendments to the statistical analyses section will not require IRB approval, unless driven by protocol or study design change. In that case a standalone SAP will be prepared prior to data lock for each analysis milestone.

7.8.1 *General Considerations*

Statistical analyses will be performed using SAS® v9.4 (SAS Institute, Cary NC, USA).

All statistical tests will be two-sided. The required significance level of findings will be equal to or lower than 5%, nominal p-values will be presented. Where confidence limits are appropriate, the confidence level will be 95%.

Continuous variables will be summarized by a mean, standard deviation, minimum, median and maximum, and categorical variables by a count and percentage. For comparison of means (continuous variables), the two-sample t-test or the Wilcoxon rank sum test will be used as appropriate. For comparison of proportions (categorical variables), the Chi-squared test or Fisher's exact test will be used as appropriate.

If multiple measurements are taken in a single patient, statistics described below will be appropriately modified to accommodate the within patient correlation.

7.8.2 *Significance levels and handling of type I error*

7.8.2.1 *Type I Error*

The overall significance level for this study is 5% using two-tailed tests, except for treatment by site interaction that will be tested at a significance level of 10%.

7.8.2.2 *Hierarchy Approach for Secondary Endpoints Analysis*

The hierarchy approach will be adopted for the primary and secondary endpoints to control type I error due to multiple endpoint testing. Thus, the primary endpoint will first be analyzed and only if $p < 0.05$, will the secondary endpoints be analyzed.

7.8.3 *Demographic and Other Baseline Characteristics*

Demographic and baseline condition related characteristics will be tabulated and compared between the study groups by data type. Continuous variables will be summarized by a mean, standard deviation, minimum, median and maximum, and categorical variables by a count and percentage.

This data will include:

- Demographic data
- Medical history
- Migraine preventive medication
- Other concomitant medication
- Migraine attacks characteristics per ICHD-3 diagnostic criteria for migraine with and without aura
- Physical examination
- Laboratory (pregnancy) tests for women of childbearing potential

7.8.4 *Disposition of Patients*

The numbers of patients who entered the study and completed each stage of the study will be provided per month, as well as the reasons for all post randomization discontinuations, grouped by major reason, e.g., lost to follow-up, adverse event, poor compliance, did not administer any treatment (with reasons). A list of discontinued patients, protocol deviations, and patients excluded from the performance analysis will be provided as well.

7.8.5 *Performance Analyses*

Primary Performance Analyses:

The primary endpoint is freedom from pain at 2 hours post treatment without rescue medications in at least 50% of treated attacks, a count and percentage of subjects free from pain will be calculated and presented for both study groups each with a two-sided 95% exact confidence interval. The groups will be compared with a chi-squared test.

If the null hypothesis is rejected in favor of the alternative hypothesis and the proportion (%) of subjects reporting freedom from pain at 2 hours post treatment without rescue medications in the treated group is greater than that of the sham group, the study will be deemed successful.

The primary endpoint will also be evaluated stratified by center using a Mantel-Haenszel test to assess the center by group interaction.

A sensitivity analysis of the primary end-point will be performed to assess the impact of missing data on the study outcome. This will be performed using several possible imputation methods.

Subset analysis:

Adjustment for other covariates such as demographics or other baseline patient characteristics may be performed by adding these variables into a logistic regression model.

Subgroup analysis according to use of preventive medications will be performed and reported by adding these variables to a logistic regression model.

Secondary performance analyses:

The secondary performance variables will be summarized by a count and percentage and compared with a chi-squared test.

Exploratory performance analyses:

A count and percentage of patients reporting freedom from pain (pain grade 0) 48 hours post treatment without rescue medications in at least 50% of treated attacks will be presented, the groups will be compared with a chi-squared test.

Use of rescue medications will be summarized by descriptive statistics per treatment group and compared between the groups with a t-test.

Patient global impression of change will be summarized by descriptive statistics per treatment group and compared between the groups with a t-test.

Ease of use will be summarized by descriptive statistics.

7.8.6 *Safety Analysis:*

The primary safety variable, the cumulative incidence (and 95% CI) of device related adverse events (AEs) throughout the study, will be presented in tabular format and will include incidence tables by severity.

Adverse event rates will be compared between the study groups with a chi-squared test.

Serious adverse events will be listed and discussed individually.

Treatment tolerability will be compared between the study groups, the number and percent of subjects who fail to complete the study and the number and percent of subjects who fail to complete the study because of Adverse Events will be presented as well.

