6.3.2 Secondary Endpoints

Secondary Performance Endpoints

1. The proportion (%) of subjects reporting treatment response at 2 hours post treatment without rescue medications in at least 50% of treated attacks. Treatment response is defined as: pain level reduction from moderate or severe at baseline to mild or pain level of none if treatment started with mild pain
2. Proportion (%) of patients reporting, 2 hours post treatment:
 - freedom from pain (pain grade 0) and their most bothersome migraine-associated symptom (MBS) in at least 50% of treated attacks
 - freedom from nausea in at least 50% of treated attacks
 - freedom from photophobia in at least 50% of treated attacks
 - freedom from phonophobia in at least 50% of treated attacks

6.3.3 Exploratory Endpoints:

1. The proportion (%) of patients reporting freedom from pain (pain grade 0) 48 hours post treatment without medications in at least 50% of treated attacks

2. The percent of subjects who are pain-free at 2 hours with no use of rescue medication, and either have no relapse of pain within the subsequent 46 hours, or, if they have a relapse of pain in this time window, it disappears every time, after two hours, using the device, with no use of rescue medications.
3. Patient global impression of change, with emphasis on disability and quality of life.

6.3.4 Safety Endpoints:

- Treatment tolerability
- Adverse events and complications whether related or unrelated to study device.

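### The hierarchy in Section 7.8.2.2 is said to control type I error over primary and secondary endpoints, but its only rule is a gate on the primary, which leaves five secondaries each tested at a nominal 5%

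*Combined protocol and SAP*

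**What the plan says.** Section 7.8.2.2 makes the claim: "The hierarchy approach will be adopted for the primary and secondary endpoints to control type I error due to multiple endpoint testing". It then gives its single operating rule: "Thus, the primary endpoint will first be analyzed and only if $p < 0.05$, will the secondary endpoints be analyzed".

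The surrounding text sets the level and the test:

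- Section 7.8.2.1: "The overall significance level for this study is 5% using two-tailed tests".
- Section 7.8.1: "The required significance level of findings will be equal to or lower than 5%, nominal p-values will be presented".
- Section 7.8.5, for the secondaries: "The secondary performance variables will be summarized by a count and percentage and compared with a chi-squared test".

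Section 6.3.2 lists five secondaries, and Section 7.2.2 makes each a binary variable. Item 1 is treatment response at 2 hours. Item 2 has four unnumbered bullets: "freedom from pain (pain grade 0) and their most bothersome migraine-associated symptom (MBS) in at least 50% of treated attacks", then freedom from nausea, from photophobia and from phonophobia.

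A separate analysis plan is mentioned in three places. Section 6.2 promises one before study start. Section 9 lists it as a document kept outside the protocol. Section 7.8 makes a standalone version conditional on a protocol or design change: "In that case a standalone SAP will be prepared prior to data lock for each analysis milestone".

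**The concern.** A gate on the primary controls error over the whole family only when the primary null is true. The trial is designed for the opposite case. Once the primary succeeds, the five secondaries open together, and the text states no order, no stop at the first failure, no split of alpha and no adjustment. As written, the rule lacks the property that the section claims for it.

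What is at stake is how the secondary results are read. A p-value below 0.05 on a symptom endpoint could be reported as error-controlled when it is not. Alternatively, an order could be chosen after the data are seen. The declaration that "the study will be deemed successful" rests on the primary alone, so the main conclusion is not at risk.

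**Working it through.** **Inputs from the documents.** Two-sided 5% (Section 7.8.2.1); 30% against 10% response, 80% power, 62 per arm (Section 7.4); five binary secondaries (Sections 6.3.2 and 7.2.2); interim look at 62 evaluable subjects and maximum 248 (Section 7.5).

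**Assumptions.** The documents give no correlations between endpoints and no expected secondary effects. I take one common correlation ρ of 0, 0.5 or 0.9 among normal test statistics. I take nausea, photophobia and phonophobia as null, and the other two secondaries as affected because they share content with the primary.

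**1. The plan's own sample size reproduces.** With pooled variance, n per arm = [1.960·√(2·0.2·0.8) + 0.842·√(0.3·0.7 + 0.1·0.9)]² / 0.2² = (1.109 + 0.461)² / 0.04 = 61.6, so 62 per arm and 124 in all. Power at 62 per arm is 80.3%. The primary test statistic is therefore given a shift of 1.960 + 0.842 = 2.802.

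**2. Where the gate works.** If the primary and all five secondaries are null, the chance of a false-positive secondary is 1.1%, 2.6% and 4.3% at ρ = 0, 0.5 and 0.9.

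**3. Where it does not.** With an effective primary and three null secondaries at ρ = 0:

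- given primary success: 1 − 0.95³ = 0.1426
- overall: 0.80 × 0.1426 = 0.1141
- favouring the device only, given success: 1 − 0.975³ = 0.0731
- favouring the device only, overall: 0.80 × 0.0731 = 0.0585

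For ρ > 0, write each statistic as √ρ·C + √(1−ρ)·e plus its shift, and integrate over the shared term C: rate = ∫ φ(c) · P(primary significant | c) · [1 − P(one null secondary not significant | c)³] dc. Dividing by 0.80 gives the rate given success.

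| At least one false-positive secondary | ρ = 0 | ρ = 0.5 | ρ = 0.9 |
|---|---|---|---|
| Overall, two-sided | 11.4% | 8.6% | 4.2% |
| Given primary success, two-sided | 14.3% | 10.8% | 5.3% |
| Overall, favouring device | 5.9% | 6.2% | 4.2% |
| Given success, favouring device | 7.3% | 7.7% | 5.2% |

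The overall two-sided rate equals 5% at ρ ≈ 0.83. The device-favouring rates compare with 2.5%, half of the two-sided 5%.

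The extreme case, all five secondaries null and independent, gives 1 − 0.95⁵ = 22.6% given success. It is unlikely, because treatment response and pain-plus-MBS freedom overlap with the primary.

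**4. Effect of the sample-size increase.** I simulated Section 7.5 with 1,000,000 draws: conditional power at the observed effect, an increase when it lies from 36% to below 80%, N raised to the smallest value that reaches 80% or to 248, and a stop if the difference is below 0. This stands in for the recalculation method the plan cites. The two-sided rates are 14.2%, 11.1% and 5.5% given success, and 11.8%, 9.2% and 4.6% overall. The adaptation changes little.

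**5. What a written rule achieves.** Same setting, given success, at ρ = 0, 0.5 and 0.9: Holm over the five secondaries gives 4.1%, 3.2% and 1.9%. A fixed sequence that happens to start with a null endpoint gives 5.0%, 4.2% and 3.1%.

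**The case against.** The strongest reply is that the rule may exist elsewhere. A detailed analysis plan was promised before study start and is kept separately, and an endpoint order is normal content for it. The word hierarchy, with secondaries numbered 1 and 2, could also mean testing in listed order, which would control the error. Part of this stands: the documents cannot show that no such rule exists. But Section 7.8.2.2 defines its hierarchy by the primary gate alone, four of the five secondaries carry no rank, and Section 7.8 makes the standalone plan conditional.

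The second reply is about size. Familywise error is properly the overall rate, so the figures given primary success overstate it. Independence is an extreme assumption for endpoints from the same patients and attacks, and three exactly null symptom endpoints beside an effective primary is a chosen scenario. This also stands. The supportable range for the two-sided overall rate runs from no excess at high correlation to a little over twice 5%.

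The third reply is that only secondaries are affected and no passage ties them to a decision. That limits the severity. It does not remove the mismatch, because the plan itself claims error control for these endpoints.

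**Conclusion.** The concern holds. As written, Section 7.8.2.2 controls error for the primary, and for the family when the primary null is true, but not among the secondaries once the primary succeeds. With three null symptom endpoints and 80% primary power, the overall chance of a false-positive secondary is 11.4% at zero correlation, 8.6% at 0.5 and 4.2% at 0.9. The correlations and the choice of null endpoints are assumptions. The gap in the text does not depend on them. The primary result, the success criterion and the sample size stand. It should be fixed, but it does not threaten the trial's main conclusion.

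**What to change.** Before the unblinded look at 62 evaluable subjects, put one of these into Section 7.8.2.2:

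1. **Holm after primary success.** Compare the five ordered p-values with 0.05/5 = 0.01, 0.05/4 = 0.0125, 0.05/3 = 0.0167, 0.05/2 = 0.025 and 0.05. No ranking is needed.
2. **Fixed sequence.** Test all five at two-sided 5% in an order the sponsor chooses and writes down. Stop at the first p ≥ 0.05 and state that later results are descriptive. Put pain-plus-MBS freedom ahead of the symptom endpoints only once capture of the most bothersome symptom is confirmed, since the PRO tables in Section 6.4.2 list no such field.
3. **Drop the claim.** Remove error control for the secondaries and label them descriptive.

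If a separate analysis plan already holds such a rule, carry it into this section.

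The change takes a few lines and no extra subjects or data. The price is power on the secondaries. As an illustration, assume each secondary alone has 80% power (the documents give none). Given primary success, power per endpoint is:

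| | ρ = 0 | ρ = 0.5 | ρ = 0.9 |
|---|---|---|---|
| Unadjusted | 80% | 86% | 94% |
| Holm | 70% | 77% | 82% |
| Last in a fixed sequence | 33% | 60% | 84% |

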Objectives	
The purpose of this study is to evaluate the safety and performance of the Nerivio Migra Migraine device for the treatment of non-chronic migraine patients with and without aura

Primary Endpoint	
Primary Performance Endpoint. Proportion (%) of patients reporting freedom from pain (pain grade 0) 2 hours post treatment without rescue medications in at least 50% of treated attacks
 
Primary Safety Endpoint. Device related adverse effects

Secondary & Exploratory Endpoints	
Performance endpoints:
 
Secondary:
 
 1. The proportion (%) of subjects reporting treatment response at 2 hours post treatment without medications in at least 50% of treated attacks. Treatment response is defined as pain level reduction from moderate or severe at baseline to mild or pain level of none if treatment started with mild pain. 2. Proportion (%) of patients reporting, 2 hours post treatment: 
 ▪ freedom from pain (pain grade 0) and their most bothersome migraine-associated symptom (MBS) in at least 50% of treated attacks ▪ freedom from nausea in at least 50% of treated attacks

	
 ▪ freedom from photophobia in at least 50% of treated attacks ▪ freedom from phonophobia in at least 50% of treated attacks 
Exploratory:
 
 3. The proportion (%) of patients reporting freedom from pain (pain grade 0) 48 hours post treatment without medications in at least 50% of treated attacks 4. The percent of subjects who are pain-free at 2 hours with no use of rescue medication, and either have no relapse of pain within the subsequent 46 hours, or, if they have a relapse of pain in this time window, it disappears every time, after two hours, using the device, with no use of rescue medications. 5. Patient global impression of change, with emphasis on disability and quality of life.
Safety Endpoints	
 • Treatment tolerability • Adverse events and complications whether related or unrelated to study device.
Patient Population	Adults 18-75 years old meeting International Headache Society criteria for migraine with and without aura, who are reporting 2-8 migraine attacks per month.
Number of Patients	Up to 248 patients with evaluable data, equally distributed between US and non-US sites

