7.6 Randomization

After a subject meets the eligibility criteria, he/she will be randomly allocated (with a 1:1 ratio) to one of the following 2 treatment groups based on a randomization scheme using the permuted block method stratified by preventive medications use and center:

- Sham Control
- Nerivio Migra group

The randomization scheme will be prepared by the study statistician using the SAS (version 9.4.) random number procedure. The block size will be fixed and study personnel will be blinded to the randomization block size.

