7.9 Pooling

Subgroup analysis of the primary performance endpoint by center, and US vs OUS, will be used to evaluate the poolability of the results. The significance of center-to-center variability in treatment effect will be evaluated by including an interaction term of treatment group by center in a logistic regression model. In the case that poolability is questionable, the reasons for differential treatment effect, such as patient and clinical characteristics, will be investigated and reported.

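### Section 7.8.5 gives two supportive analyses jobs they cannot do: a centre-stratified Mantel-Haenszel test does not assess centre-by-group interaction, and adding preventive use to a logistic model gives no effect by subgroup

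*Combined protocol and SAP*

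**What the plan says.** - **Primary test (7.8.5).** An unstratified comparison: "The groups will be compared with a chi-squared test".
- **Centre (7.8.5).** "The primary endpoint will also be evaluated stratified by center using a Mantel-Haenszel test to assess the center by group interaction".
- **Centre (7.9).** Centre-to-centre variability in the treatment effect is examined by "including an interaction term of treatment group by center in a logistic regression model". The same section adds: "Subgroup analysis of the primary performance endpoint by center, and US vs OUS, will be used to evaluate the poolability of the results".
- **Level (7.8.2.1).** The overall two-tailed level is 5%, "except for treatment by site interaction that will be tested at a significance level of 10" per cent.
- **Preventive use (7.8.5).** "Subgroup analysis according to use of preventive medications will be performed and reported by adding these variables to a logistic regression model". The sentence just before it describes adjustment for other covariates in nearly the same terms.
- **Randomisation (7.6).** A "randomization scheme using the permuted block method stratified by preventive medications use and center".

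**The concern.** In each case the stated method does not answer the stated question.

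**Centre.** The Mantel-Haenszel statistic adds observed-minus-expected responders over centres. Effects in the same direction accumulate and opposite effects cancel. A significant result is therefore no sign of interaction, and a non-significant one is no sign of homogeneity. A reader who took 7.8.5 at its word would be misled in both directions.

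**Preventive use.** A logistic model with treatment and preventive use as added terms forces the same odds ratio on users and non-users. It adjusts for preventive use but says nothing about whether the device works differently in the two groups. Preventive use is a randomisation factor and the only subgroup that 7.8.5 commits to report, so the sponsor evidently wants an answer.

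At stake is the interpretation of supportive results, not the primary claim.

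**Working it through.** **The plan's own figure.** Section 7.4 gives 10% vs 30%, two-sided 5%, 80% power. With pooled variance and no continuity correction, n per arm = [1.96·√(2·0.2·0.8) + 0.842·√(0.21 + 0.09)]² / 0.20² = (1.109 + 0.461)² / 0.04 ≈ 61.6. This rounds up to 62 per arm, or 124 in total, with 80.3% power. The plan's figure reproduces, and nothing below changes it.

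**Mantel-Haenszel, worked by hand.** Take two centres with 31 per arm each (an assumed layout totalling 124).
- *Opposite effects:* active vs sham responders are 9 vs 3 in one centre and 3 vs 9 in the other, with odds ratios (9·28)/(3·22) = 3.82 and 0.26. Active responders total 12 and the expected number is 6 + 6 = 12, so the statistic is 0.00 (p = 1.00). Homogeneity is nevertheless rejected: the Woolf chi-squared is 6.83 (p = 0.009), and the likelihood-ratio test of the product term is 7.72 (p = 0.005).
- *Equal effects:* 9 vs 3 in both centres. Observed minus expected is 18 − 12 = 6. The variance per centre is 31²·12·50/(62²·61) = 2.459, so the statistic is 36/4.918 = 7.32 (p = 0.007), with no interaction at all.

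**Mantel-Haenszel, simulated.** Same layout. The 10% level is the one that 7.8.2.1 sets for site interaction, applied here to both tests.

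| True rates, active vs sham | Mantel-Haenszel rejects | Interaction test rejects (likelihood-ratio / score) |
|---|---|---|
| 30% vs 10% in both groups | 89% | 13% / 11% |
| 50% vs 10% in one, 10% vs 10% in the other | 91% | 63% / 67% |
| 30% vs 10% in one, 10% vs 30% in the other | 9% | 89% / 89% |

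**Preventive use.** The documents do not give the share of users. Assume about 35%, so 40 non-users and 22 users per arm. Suppose the sham rate is 10% throughout, and the active rate is 41% in non-users and 10% in users. The overall active rate is (40·0.41 + 22·0.10)/62 = 30%, as planned. The true odds ratios are (0.41/0.59)/(0.10/0.90) = 6.25 and 1.00. The additive model fitted to these rates gives a single odds ratio of 4.05, and fitted rates in users of 4% (sham) vs 16% (active), where the truth is 10% in both.

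An interaction term at 10% would detect this pattern 46% (likelihood-ratio) to 50% (score) of the time. At 30% vs 10%, the 95% half-width for a subgroup difference is 1.96·√(0.30/m):
- non-users (m = 40): ±17 points
- users (m = 22): ±23 points
- difference between the two: 1.96·√(0.30·(1/40 + 1/22)) = ±28 points

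**Stratifying the primary test.** Compare chi-squared with a Cochran-Mantel-Haenszel (CMH) test over four strata (preventive use by US/non-US; 35% users assumed, region not prognostic), with overall rates of 10% vs 30%. Type I error is taken at 20% in both arms.

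| Assumed log odds ratio for preventive use | Power, 62 per arm | Power, 68 per arm with 10% random drop-out |
|---|---|---|
| 0 | 81.0 → 81.3% | 81.3 → 81.0% |
| −1 | 81.4 → 82.6% | 81.4 → 81.9% |
| −2 | 81.7 → 84.2% | 81.8 → 83.6% |

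The change is −0.3 to +2.5 points. The chi-squared type I error is 4.7, 4.5 and 3.9% with equal arms, and 5.0, 4.9 and 4.3% with drop-out. The CMH test stays at 4.9 to 5.1%. A more extreme assumption (two equal strata, sham rates 2% and 18%, common odds ratio) gives 68.8 → 74.3%, so the gain depends on a prognostic strength that the documents do not state.

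**The case against.** **Centre heterogeneity is already handled.** Section 7.9 names a treatment-by-centre term, 7.8.2.1 sets its level, and 7.9 says what follows if poolability is doubtful. Without its last clause, the 7.8.5 sentence describes an acceptable centre-adjusted analysis. This objection stands. A reader might infer from 7.8.5 that centre heterogeneity goes untested; section 7.9 shows that it does not.

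**The illustrations rest on assumptions.** The two-group layout is not the plan's: the number of centres is not stated. Nor can the layout be taken from the synopsis as an equal regional split at 124. The synopsis ties "equally distributed between US and non-US sites" to a maximum of 248, and 7.4 requires only that at least half be from the US. The exactly opposite case is an extreme. This also stands, but what the Mantel-Haenszel statistic measures does not depend on the layout.

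**The preventive-use sentence is merely ambiguous.** It promises a subgroup analysis, and a main-effects model would not be one, so an interaction may have been meant. This is only partly persuasive. The preceding sentence uses nearly the same words for ordinary covariate adjustment, and 7.9 says interaction when it means interaction. No other section supplies the missing term.

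**The primary test should be left alone.** A reader might infer that chi-squared is invalid because it ignores the randomisation factors. The calculations do not support that: its type I error is at or below about 5%. Section 7.5 also calls for the conventional test at the final analysis. Stratifying is therefore an option, not a correction.

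**Conclusion.** The point holds as a correction to two supportive analyses in 7.8.5, with low severity. The Mantel-Haenszel test is given a purpose it cannot serve, although 7.9 covers the question. The preventive-use analysis, as written, yields one adjusted odds ratio and no effect by subgroup, and this gap is covered nowhere else.

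Both conclusions follow from the methods named and need no assumption. The sizes shown do: the two-centre layout, 35% preventive users, the all-or-none subgroup effect and the prognostic strengths are all illustrative. Even when properly specified, the preventive-use analysis would be imprecise, so it can only be supportive.

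The documents do not support the wider inference that the sample size, the type I error or the success rule is at risk.

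**What to change.** 1. **Centre, 7.8.5.** Describe the centre-stratified Mantel-Haenszel test as a centre-adjusted sensitivity analysis of the treatment effect. Refer heterogeneity between centres to the treatment-by-centre term in 7.9, at the 10% level in 7.8.2.1.
2. **Preventive use, 7.8.5.** Add a treatment-by-preventive-use interaction term. Report the treatment difference with its 95% confidence interval separately in users and non-users, labelled supportive.
3. **Optional.** Report a CMH test stratified by the 7.6 factors, with small centres pooled, beside the chi-squared test. If it replaces chi-squared as the primary test, the conditional-power calculation in 7.5 should use the same statistic.

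Items 1 and 2 need only wording and routine code, with no new data or patients. Section 7.8 says that changes to the statistical section do not need IRB approval unless a protocol or design change drives them. The changes are best fixed before the interim data are unblinded. Replacing the primary test under item 3 would also mean rechecking the interim rules.
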